10.4 Administration of chemotherapy

The sponsor will not provide the chemotherapy (AVD) as it is considered as standard care for Hodgkin lymphoma. Chemotherapy products are to be used according to summary of product characteristics.

10.4.1 Doxorubicin

Doxorubicin is an anthracycline antibiotic that binds tightly with DNA, inhibits nucleic acid synthesis and causes DNA strand breaks. Although active throughout the cell cycle, cells in S phase are most sensitive. Common side effects include myelosuppression, alopecia, and stomatitis, which is dose related

and may be severe. Drug-induced cardiomyopathy which may result in congestive heart failure, is a cumulative dose-dependent effect and risk becomes considerable at total doses exceeding 500 mg/m2. Doxorubicin is given intravenously and is a vesicant causing severe local necrosis at the site of injection if extravasation occurs. Nausea and vomiting are frequent.

10.4.2 Vinblastine

Vinblastine is the salt of an alkaloid derived from Vinca rosea Linn, a common herb known as the periwinkle. Mechanism of Action: Tissue culture studies suggest an interference with metabolic pathways of amino acids leading from glutamic acid to the citric acid cycle and to urea. A number of studies in vitro and in vivo have demonstrated its stathmokinetic effect and various atypical mitotic figures. Other studies indicate an effect on cell energy production required for mitosis and the interference with nucleic acid synthesis. Reversal of antitumor effect by glutamic acid and tryptophan has been observed.

Leukopenia is the usual dose-limiting side effect, with the nadir falling four to seven days post-injection. Thrombocytopenia and anemia may occur. Gastrointestinal toxicities include nausea, vomiting, diarrhea or constipation, abdominal pain, ileus, peptic ulcer, rectal bleeding and anorexia. Fever and phlebitis have also been seen when the drug is given as an infusion. Extravasation may lead to tissue necrosis. Ten percent of the patients will experience peripheral neuropathy. Alopecia can also occur.

10.4.3 Dacarbazine (DTIC)

Three hypotheses have been offered as the mechanism(s) of action of DTIC: inhibition of DNA synthesis by acting as a purine analog, action as an alkylating agent, and/or interaction with SH groups.

Myelosuppression is the dose-limiting toxicity. The predominant side effect observed in humans has been anorexia, nausea and vomiting. This occurs with maximal intensity on the first day of a five-day course, and in many patients, it is less with each subsequent day. Myelosuppression consisting of thrombocytopenia and leukopenia occurs in approximately one-quarter of patients after a five-day course of 250 mg/m2. The time course for this myelosuppression is generally maximal approximately three weeks after administration with the period of recovery variable. Other reported side effects include infrequent flu-like syndrome associated with fever and myalgia, phlebitis, liver necrosis, hepatic toxicity, anaphylaxis, photosensitivity, alopecia, and facial flushing. Rarely, DTIC has caused diarrhea.

10.5 Drugs description, storage and handling

10.5.1 Description of investigational product: Brentuximab Vedotin (NSC 749710)

Other Names: AdcetrisTM, SGN-35

Classification: Monoclonal Antibody CAS

Registry Number: 914088-09-8

M.W.: 153 kDa

Mode of Action: A CD-30 directed antibody-drug conjugate (ADC) consisting of 3 components: (1) the chimeric IgG1 antibody cA10, specific for human

CD30, (2) the microtubule disrupting agent monomethyl auristatin E (MMAE), and (3) a protease-cleavable linker that covalently attaches MMAE to cA10. Its cytotoxic activity occurs when ACD binds to the CD-30 expressing cell, forming an ADC-CD30 complex compound and releasing MMAEs via proteolytic cleavage. Subsequently, MMAE binds to tubulin to disrupt the microtubule network within the cells, resulting in cell cycle arrest and apoptosis.

Preparation: Consists of 2 steps: dilution of the stock solution and dilution of the final solution.

- Step 1: To make a 5 mg/mL concentration.
 - 1. Reconstitute the 50 mg lyophilized powder SGN-35 with 10.5 mL Sterile Water for Injection, USP. Final concentration is 5 mg/mL (Note: total volume is 11 mL).
 - 2. Swirl the vial gently. Do not shake.
 - 3. Let the reconstituted vial settle for one minute to eliminate bubbles. The reconstituted solution should be colorless, clear to slightly opalescent and should NOT have visible particulates.
 - 4. Store the reconstituted vial under refrigeration (2– 8°C), protect from light if not used immediately. Discard after 8 hours.
- Step 2: Further dilute the IV solution. Use vials from the same Lot number for each dose.
 - 1. Withdraw the calculated amount of drug from the 5 mg/mL reconstituted vial in step 1.
 - Inject the required amount of drug into a 50 mL to 250 mL of 0.9% NS, Lactated Ringer's Solution, USP, or dextrose 5% in Water (D5W), USP to a final concentration between 0.4 – 1.8 mg/mL.
 - 3. Brentuximab vedotin solution is compatible in polyvinylchloride (PVC), ethylene vinyl acetate (EVA), polyolefin, or polyethylene.
 - 4. Do not shake. Gently invert the bag.
 - 5. The prepared IV bag is to be stored at 20 80 C and must be used within 24 hours of initial product reconstitution. Protect the prepared IV solution from direct sunlight if not used immediately.
 - 6. Prior to administration, inspect the IV bag for discoloration or floating particulates. Do not use the IV solution if the solution is discolored or/and have particulates.

CAUTION: The single-use lyophilized dosage form contains no antibacterial preservatives. Therefore, it is advised that the reconstituted product be discarded 8 hours after initial entry.

Route(s) of Administration: Intravenous. Do not administer as an IV Push or bolus.

Method of Administration: Infuse the prepared IV solution over 30 minutes. Do not mix with other medications. Do not use an in-line filter for the IV administration. The IV bag does NOT need light protection during the IV administration.

Patient Care Implications:

• New signs and symptoms of CNS system abnormalities may indicate progressive multifocal leukoencephalopathy (PML).

- Tumor lysis syndrome, particularly in patients with highly proliferative tumors or high tumor burden prior to treatment.
- Infusion-related reactions, including anaphylaxis, may occur. Refer to protocol for the management of infusion- related reactions.
- Signs and symptoms of peripheral neuropathy such as tingling or numbress of the hands, feet, or any muscles weakness.
- Steven-Johnson syndrome
- High fever $(\geq 38^{\circ}C)$ or other signs of potential infection.
- 10.5.2 Packaging and labelling

SGN-35 will be supplied as a single use, preservative free vial containing 50 mg of white to off-white lyophilized powder for Injection. Inactive ingredients are trehalose, sodium citrate, and polysorbate 80. The pH is 6.6 once reconstituted in Sterile Water for Injection.

Study drug labels will contain information to meet the applicable regulation requirements. The investigational product will be labelled as open label material.

10.5.3 Storage conditions and handlings

Storage: Store the intact vials refrigerated at 2-8°C. Protect from direct sunlight.

Stability: The stability testing of the intact vials is ongoing. Reconstituted agent must be diluted and administer within 24 hours.

Refer to investigator brochure for additional information regarding storage and handling.

10.6 Dose adjustments

- 10.6.1 Brentuximab Vedotin Dose Modifications
 - 10.6.1.1 Intrapatient. Dose Reductions for Starting Dose of 1.2 mg/kg Every 2 Weeks

No further dose reductions will be permitted beyond 0.6 mg/kg of brentuximab vedotin. Patients not tolerating a dose of 0.6mg/kg will continue with standard dose AVD at the discretion of the investigator.

Dose Level:

- 1.2 mg/kg
- 0.9 mg/kg
- 0.6 mg/kg
- 10.6.1.2 Treatment Modification Guidelines for Brentuximab Vedotin for All Cycles

Event	CTCAE.v4.0 Grade	Action to be Taken
Allergic reactions, or Acute infusional reactions/cytokine release syndrome	Grade 1-2	 For first reaction: Hold the infusion and wait 30 to 60 minutes (depending upon the reaction severity) Treat reactions with diphenhydramine 1 mg/kg (max 50 mg), or follow local institution guidelines. Depending on the reaction severity, dexamethasone 0.2mg/kg (max 10mg) IV should be used or follow local institutions guidelines. Upon resolution of the symptoms, at the physician's discretion, it may be possible to resume treatment by administering an H2 blocker approximately 30 minutes before restarting the infusion. paracetamol can also be considered. Brentuximab vedotin may be administered at half of the previously administered rate at the discretion of the investigator. For subsequent doses: Utilize diphenhydramine with or without paracetamol as pretreatment for all subsequent infusions. Dosing will be administered over the shortest infusion period that was well tolerated. If Grade 1-2 infusion reactions recur despite the above measures, either during re- challenge or subsequent treatments: Take the measures outlined above With subsequent dosing, add dexamethasone 0.2 mg/kg (max 10mg) IV or equivalent to medications above prior to infusion.
	Grade 3	 Stop infusion immediately Administer diphenhydramine hydrochloride 1 mg/kg IV (max 50 mg), dexamethasone 0.2mg/kg (max 10mg) IV (or equivalent), bronchodilators for bronchospasms, and other medications as medically indicated Once symptoms recover, brentuximab vedotin should not be resumed for that course Subsequent courses of brentuximab vedotin may be considered at physicians' discretion, after a discussion and approval by one of the French coordinator. All subsequent infusions will use the following premedications prior to infusion, diphenhydramine hydrochloride 1 mg/kg IV (max 50 mg), dexamethasone 0.2mg/kg (max 10mg) IV (or equivalent). In addition, the infusion will be administered at 50% of the previous infusion rate
	Grade 4	 Stop infusion immediately Administer diphenhydramine hydrochloride 1 mg/kg (max 50mg) IV, dexamethasone 0.2 mg/kg (max 10mg) IV (or equivalent), and other anaphylaxis medications as indicated Adrenaline or bronchodilators at the discretion of the investigator will be administered as indicated. Hospital admission for observation may be indicated. Discontinue brentuximab vedotin
Anaphylaxis	Any Grade	• If anaphylaxis occurs, immediately and permanently discontinue administration of brentuximab vedotin and administer appropriate medical therapy.

Event	CTCAE.v4.0 Grade	Action to be Taken
Pancreatitis	Grade 2	 Withhold dose until toxicity has returned to baseline, then continue on protocol therapy but resume at one dose reduction. If Grade 2 pancreatitis recurs after one dose reduction, the patient must be removed from protocol therapy.
	Grades 3-4	• Permanently discontinue brentuximab vedotin.
Peripheral Neuropathy	Grade 1	Continue at same dose level.
	Grade 2	 Treatment is to be delayed until neuropathy improves to Grade 1 or baseline Brentuximab vedotin will be reduced by one dose level for subsequent treatments once peripheral neuropathy returns to baseline or returns to grade 1. Patients who experience a delay of over 7 days in cycle 1 will be removed from the study. For subsequent cycles, if two sequential doses of brentuximab vedotin are held due to unresolved toxicity, leading to a treatment delay of an additional 2 weeks (i.e., 4 weeks between doses), participant will discontinue brentuximab vedotin. Participants will have the option to discontinue protocol therapy or continue study with AVD with dose adjustments in vinblastine as clinically necessary based on the level of neuropathy on the day of treatment as per standard label/summary product characteristics.
	Grade 3	 Treatment is to be delayed until neuropathy improves to Grade 1 or baseline. Brentuximab vedotin will be reduced by one dose level for subsequent treatments once a peripheral neuropathy returns to baseline or returns to grade 1. Patients who develop grade 3 neuropathy after dose reduction will have to discontinue brentuximab vedotin. Subjects will have the option to be taken off protocol or continue study with AVD with dose adjustments as clinically necessary. Patients who experience a delay of over 7 days in cycle 1 will be removed from the study. For subsequent cycles, if two sequential doses of brentuximab vedotin are held due to unresolved toxicity, leading to a treatment delay of an additional 2 weeks (i.e., 4 weeks between doses), the participant will discontinue protocol therapy or continue study with AVD with dose adjustments in vinblastine as clinically necessary, based on the level of neuropathy on the day of treatment as per standard label/Summary product characteristics.
	Grade 4	Discontinue brentuximab vedotin.
Neutropenia occurring on the day of treatment	Grade 1-2	Continue at same dose level.

Event	CTCAE.v4.0 Grade	Action to be Taken
	Grade 3-4	 Reinstitute growth factor support (GCSF) for treatment of neutropenia until recovery to ANC ≥1,000/mm3. If myeloid growth factor support was inadvertently omitted in the previous dose, patients should receive the same full dose of brentuximab vedotin in the next treatment dose, along with myeloid growth factor support If, as per protocol, the participant was on myeloid growth factor support with the previous dose and presents with treatment day neutropenia, reinstitute myeloid growth factor support (GCSF) until recovery to ANC ≥1,000/mm3 and reduce brentuximab vedotin one dose level for all remaining cycles. Dose reduction below brentuximab vedotin 0.6 mg/kg is not allowed. Brentuximab vedotin should not be given for any subsequent cycles. If participants have febrile neutropenia, please see Section 10.6 for dose modifications.
Thrombocytopenia	Grade 1-2	Continue at same dose level.
	Grade 3-4	 Withhold dose until toxicity is ≤ Grade 2 or has returned to baseline, then continue on protocol therapy but at one dose reduction Patients who experience Grade 3-4 thrombocytopenia after dose reduction must be removed from protocol therapy Patients who experience a delay of over 7 days in cycle 1 will be removed from the study. For subsequent cycles, if two sequential doses of brentuximab vedotin are held due to unresolved toxicity, leading to a treatment delay of an additional 2 weeks (i.e., 4 weeks between doses), the patient will be taken off protocol therapy.
Lymphopenia	Grade 1-4	Continue at same dose level.
Non-hematologic ^a events (not including electrolyte abnormalities) or febrile neutropenia) (See Section 10.6.1.5 for treatment modifications for febrile neutropenia)	Grade 1-2	Continue at same dose level.

Event	CTCAE.v4.0 Grade	Action to be Taken
	Grade 3-4	 Withhold dose until toxicity is ≤ Grade 2 or has returned to baseline, then continue on protocol therapy but resume at one dose reduction of brentuximab vedotin. If non-hematological Grade 3-4 toxicity recurs after one dose reduction, the patient must be removed from protocol therapy Patients who experience a delay of over 7 days in cycle 1 will be removed from the study. For subsequent cycles, if two sequential doses of brentuximab vedotin are held due to unresolved toxicity, leading to a treatment delay of an additional 2 weeks (i.e., 4 weeks between doses), the patients will be taken off protocol therapy, and brentuximab vedotin will be discontinued. Participants will have the option to be taken off protocol or continue study with just AVD without brentuximab vedotin.
Electrolyte Abnormalities	Grade 1-4	 Continue at same dose level, provided electrolyte toxicity is not medically consequential and has been readily corrected If electrolyte abnormality is medically consequential, refer to guidelines above for non-hematologic events

^a Patients who develop Grade 3 or 4 electrolyte laboratory abnormalities may continue study treatment without interruption but should receive appropriate medical therapy at the discretion of the investigator.

^b GCSF will be administered on Days 2-10 and 16-24 throughout each 28-day cycle using standard doses. Pegfilgrastim may be substituted for GCSF and administered on days 2 and 16.

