	Grade 3	 Treatment is to be delayed until neuropathy improves to Grade 1 or baseline. Brentuximab vedotin will be reduced by one dose level for subsequent treatments once peripheral neuropathy returns to baseline or returns to a grade 1. Participants who develop grade 3 neuropathy after dose reduction will have to discontinue brentuximab vedotin. Participants will have the option to be taken off protocol or continue study with AVD with dose adjustments as clinically necessary. Participants who experience a delay of over 7 days in cycle 1 will be removed from the study. For subsequent cycles, if two sequential doses of brentuximab vedotin are held due to unresolved toxicity, leading to a treatment delay of an additional 2 weeks (i.e., 4 weeks between doses), the participants will discontinue brentuximab vedotin. Participants will have the option to discontinue protocol therapy or continue study with AVD with dose adjustments in vinblastine as clinically necessary, based on the level of neuropathy on the day of treatment as per standard label/Summary product characteristics. 	

Event	CTCAE v5.0	Action to be Taken	
	Grade		
	Grade 4	Discontinue brentuximab vedotin.	
Neutropenia	Grade 1-2	Continue at same dose level.	
Occurring on the Day of Treatment ^b	Grade 3-4	 Reinstitute growth factor support (GCSF) for treatment of neutropenia until recovery to ANC ≥1,000/mm³. If myeloid growth factor support was inadvertently omitted in the previous dose, participants should receive the same full dose of brentuximab vedotin in the next treatment dose, along with myeloid growth factor support. If, as per protocol, the participant was on myeloid growth factor support with the previous dose and presents with treatment day neutropenia, reinstitute daily growth factor support (GCSF) until recovery to ANC ≥1,000/mm³ and reduce brentuximab vedotin one dose level for all remaining cycles. Dose reduction below brentuximab vedotin 0.6 mg/kg is not allowed. Brentuximab vedotin should not be given for any subsequent cycles. 	
Thrombocytopenia	Grade 1-2	Continue at same dose level.	

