10.6.2 AVD-Brentuximab Vedotin Dose Modifications (applies to all cycles)

Hematologic Toxicity	Although it is common practice to attenuate doses or delay treatment due to cytopenias alone, recent studies have shown that in the non-HIV setting for cHL patients receiving delays results in suboptimal treatment outcomes ^{77,78} . Patients should receive full doses of AVD on schedule on Days 1 and 15 of each 28-day cycle without treatment delays, unless neutropenic fever or documented infections are present.
Febrile Neutropenia	If febrile neutropenia occurs, then prophylaxis with antibacterial therapy is recommended for the subsequent cycle (e.g., levofloxacin 500 mg PO daily, Days 6-13 and Days 20-27 unless neutropenia occurred earlier in the cycle). Continued antibacterial antibiotic use thereafter is at the discretion of the treating physician. If a second febrile neutropenia episode occurs, decrease the doses of vinblastine and doxorubicin to 75% of the previous dose received for the next cycle (in addition to above antibiotic and GCSF supportive care measures). Re-escalation is at the discretion of the treating physician. If a third episode of febrile neutropenia occurs, patients should be maintained on therapy with supportive measures unless infection is life threatening.
Transfusions	Erythrocyte and platelet transfusions will be administered as needed at the discretion of the treating physician.
Severe Infection	Severe infection (NCI CTC Version 5.0, Grade 3 or 4) due to chemotherapy- related neutropenia requires a decrease in the doses of vinblastine and doxorubicin to 75% of the last dose received for the next cycle. Re-escalation is at the discretion of the treating physician.

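### In both protocols the Grade 3-4 treatment-day neutropenia row ends with a stop on brentuximab vedotin that carries no printed condition and, read literally, conflicts with the one-level reduction ordered just before it

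*Combined protocol and SAP*

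**What the plan says.** The row covers Grade 3-4 neutropenia on the day of treatment. It stands in the AMC protocol, Table 5-A (Section 5.1), and in the French protocol, Section 10.6.1.2, with the same instructions in the same order:

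1. Growth factor is reinstituted until the neutrophil count recovers to at least 1,000/mm³.
2. One branch covers omitted growth factor: "If myeloid growth factor support was inadvertently omitted in the previous dose, patients should receive the same full dose of brentuximab vedotin".
3. The other branch, for growth factor given as planned, says to "reduce brentuximab vedotin one dose level for all remaining cycles".
4. The floor follows: "Dose reduction below brentuximab vedotin 0.6 mg/kg is not allowed".
5. The row then says: "Brentuximab vedotin should not be given for any subsequent cycles".

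In the AMC table, items 3 and 4 run on directly: "reduce brentuximab vedotin one dose level for all remaining cycles. Dose reduction below brentuximab vedotin 0.6 mg/kg is not allowed". Item 5 follows there too, again with no condition.

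The opening of the same section bears on how item 5 is read. French Section 10.6.1.1 says "No further dose reductions will be permitted beyond 0.6 mg/kg of brentuximab vedotin" and then "Patients not tolerating a dose of 0.6mg/kg will continue with standard dose AVD at the discretion of the investigator". AMC Section 5.1 opens with the same two rules.

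**The concern.** Item 3 keeps the participant on brentuximab vedotin at a lower level to the end of treatment. Item 5, taken as printed, gives none in any later cycle. A participant at 1.2 or 0.9 mg/kg cannot receive both. At 0.6 mg/kg there is no clash, because item 4 already rules out a further reduction.

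Brentuximab vedotin is the study drug. The primary result is the 2-year PFS of the regimen, estimated in 51 participants, and the toxicity results describe the same regimen. If sites apply different sentences of the row, participants with the same count at the same dose level receive materially different treatment, and the pooled estimate describes a mixture that the plan did not intend.

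**Working it through.** The plan gives no figure of its own here. The check is a reading of the row, followed by simple exposure arithmetic.

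**Two readings, starting at 1.2 mg/kg with growth factor given**

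| Event | Item 5 tied to the 0.6 mg/kg floor | Item 5 standing alone |
|---|---|---|
| First | 0.9 mg/kg for remaining cycles | 0.9 mg/kg for remaining cycles *and* none in later cycles |
| Second | 0.6 mg/kg | not reached |
| Third | no brentuximab vedotin | not reached |

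On the left, the reduction and the stop fall at different dose levels and do not conflict. On the right, they collide at the first event.

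**Text that bears on the choice**

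- *For the left column:* item 5 directly follows the floor sentence. The section opening (AMC 5.1; French 10.6.1.1) has participants who do not tolerate 0.6 mg/kg continue on AVD. The ladder printed for febrile neutropenia (AMC 5.1.3; French 10.6.1.5) runs 1.2, 0.9, 0.6, then 0 mg/kg.
- *Against assuming it:* in the same table, Grade 3-4 thrombocytopenia after dose reduction, and recurrence of Grade 3-4 non-hematologic toxicity after one reduction, end protocol therapy without a descent to 0.6 mg/kg. Those rows print their trigger. The neutropenia row does not.

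**Exposure for a single event on Cycle 1 Day 15**

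Inputs: 6 cycles with 2 doses each, at 1.2 mg/kg; next level down 0.9 mg/kg. This is the earliest treatment day that has a previous dose. Every other dose is assumed given as planned. The row does not say what happens to the dose due that day, so three cases are carried for both readings: held (0), reduced (0.9) or full (1.2).

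- Planned: 12 × 1.2 = 14.4 mg/kg.
- Reduce: 1.2 + {0, 0.9, 1.2} + 10 × 0.9 = 10.2, 11.1 or 11.4 mg/kg. Divided by 14.4, this is 70.8%, 77.1% or 79.2%.
- Stop: 1.2 + {0, 0.9, 1.2} = 1.2, 2.1 or 2.4 mg/kg. Divided by 14.4, this is 8.3%, 14.6% or 16.7%.

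In each case the gap is 10 × 0.9 = 9.0 mg/kg, or 62.5% of plan. It shrinks for later events. On Cycle 4 Day 15, four doses remain, so it is 4 × 0.9 = 3.6 mg/kg, or 25%.

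**The case against.** The strongest reply is that the text has a coherent reading. The stop follows the floor, the section opening and the ladder agree with it, and the literal reading leaves the one-level reduction and the floor with almost nothing to govern. This stands. A reader might infer a flat contradiction, and the documents do not support that.

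What the reply does not do is put the condition into the row. A site must infer it, in a table where other rows stop therapy after one reduction.

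Four further inferences are tempting and are not made here:

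- **A breach of the on-schedule rule.** French Section 10.6.2 and AMC Section 5.2.1 require treatment "without treatment delays, unless neutropenic fever or documented infections are present", but that rule concerns AVD. The neutropenia row orders no hold. Other rows say so when they want a dose withheld or delayed, and here the recovery threshold qualifies only the growth factor. A removal for a delay of over 7 days in cycle 1 would therefore follow from a wait that this row does not order.
- **A second contradiction over the dose due that day.** The row is silent on it. That is missing detail.
- **A count of affected participants.** The 74% Grade 3/4 neutropenia in the background sections pools 31 patients, of whom 25 received ABVD and 6 received AVD with brentuximab vedotin. It also counts events at any time, not on treatment days. The documents give no treatment-day rate under growth factor.
- **Loss of progression follow-up.** The literal reading leaves one or two doses, and a rule in the febrile neutropenia section ends study therapy for those unable to receive at least 4. Whether that rule reaches this row is not stated, so nothing is rested on it.

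**Conclusion.** The point holds as a missing condition in a dosing row, present in both protocols. Followed exactly as printed, the row gives incompatible orders to a participant at 1.2 or 0.9 mg/kg. Followed with the floor sentence and the section opening, it does not. The documents favor the second reading without stating it.

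The size can be given per participant only. A single Cycle 1 Day 15 event leaves 10.2-11.4 mg/kg (71-79% of plan) under one reading and 1.2-2.4 mg/kg (8-17%) under the other. These figures assume a 1.2 mg/kg start, no other modification and no second event, and they are close to the largest gap the row can produce. Neither the number of participants who will meet the row nor the share of sites that would read it literally can be derived, so no effect on the PFS estimate is claimed. Because the ambiguity concerns delivery of the study drug and is easily cured, it should be corrected.

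**What to change.** Reconcile AMC Section 5.1 and Table 5-A with each other, and French Sections 10.6.1.1 and 10.6.1.2 likewise, by stating in the neutropenia row the condition under which its last sentence applies. Use the same wording in both protocols, since the data are pooled. While amending, the sponsor may also state what happens to the brentuximab vedotin due on the day of the low count. The sponsor's clinicians decide both rules; this review takes no position on either.

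The cost is one or two sentences in each dose table, taken through the usual amendment approvals. No new data, participants or analyses are needed.
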